4.2.4.4 Supportive Analysis of DoR Endpoint

A supportive analyses of DoR for Part B will be presented using Investigator responses and based on modified Lugano criteria and RECIL. Data will be recorded in eCRF.

4.2.5 Secondary Endpoint: Duration of Complete Response (DoCR)

DoCR is a secondary endpoint for Part A Dose Escalation and Part B Dose Expansion. Responses assessed by Investigator for Part A using modified Lugano and RECIL criteria; and by BICR for part B using modified Lugano.

4.2.5.1 Definition

DoCR is defined as the time from the date of first documented complete response (CR) until date of first documented relapse/disease progression per Lugano and RECIL criteria as assessed by Investigator (or by BICR for Part B) at local site or death (by any cause in the absence of disease progression).

4.2.5.2 Derivations

DoCR (months) = (date of progression free survival [PFS] event [progression/death] or censoring – date of first complete response + 1) / (365.25/12).

The end of response should coincide with the date of progression or death from any cause used for the PFS endpoint. The time of the initial response is defined as the latest of the dates contributing towards the first visit response of CR. If a participant does not progress following a response, then their DoCR is censored on the PFS censoring date. Only participants who have achieved objective response are evaluated for DoCR.

4.2.5.3 Analysis of Secondary Endpoint: DoCR

The analysis of DoCR will include all participants in the response-evaluable analysis set. Only participants who achieved complete response will be included in the summaries of DoCR.

Kaplan-Meier plots of DoCR with at least responders per dose level may be presented if data permitted. The median DoCR and 2 sided 95% CI will be estimated and graphically presented using the Kaplan-Meier method. In addition, percentage of participants remaining in response at 3, 6, 12, 18 and 24 months after initial response may also be presented. These time points may be adjusted according to actual data observed in the study without amendment to this SAP. Reasons for censoring for DoCR will also be summarized.

Swimmer plots by participant (including non-complete responders) may be created to visualise when complete response begins and ends and when study intervention is withdrawn.

4.2.5.4 Supportive Analysis of DoCR Endpoint

A supportive analyses of DoCR for Part B will be presented using Investigator responses and based on modified Lugano criteria and RECIL. Data will be recorded in eCRF.

4.2.6 Secondary Endpoint: Progression-free Survival (PFS)

PFS is a secondary efficacy endpoint for Part A Dose Escalation and Part B Dose Expansion. Responses assessed by Investigator for Part A using modified Lugano and RECIL criteria; and assessed by BICR for part B, using modified Lugano.

4.2.6.1 Definition

PFS is defined as the time from first dose until the earlier of the date of first documented disease progression, per Lugano classification (and per RECIL) as assessed by the investigator for Part A (by BICR per Lugano classification for Part B), or death (by any cause in the absence of disease progression or subsequent anticancer treatment or bone marrow transplantation in response).

4.2.6.2 Derivations

PFS (months) = (date of PFS event [progression/death] or censoring – date of first dose + 1) / (365.25/12).

Participants who have not progressed or died at the time of analysis, or have unknown status, are censored at the time of the latest date of assessment from their last evaluable disease assessment. However, if the participant progresses or dies immediately after two or more consecutive missed visits, the participant is censored at the time of the latest evaluable disease assessment prior to the two missed visits. Note: a NE visit is not considered as a missed visit.

If the participant has no evaluable disease assessments post-baseline or does not have baseline tumor assessment data they are censored at Day 1, unless they die within 57 weeks (i.e, 2 missed visit after Year 1 whereby disease assessments are every 6 months [2 x 26 weeks + 5 week for late visit = 57 weeks]) then the death qualifies as a PFS event. Participants who are censored at Day 1 are included in the FAS and the analysis but they do not contribute to any risk set. For participants who met one or more censoring conditions, PFS will be censored according to the earliest censoring condition; for participants who met none of the censoring conditions, PFS will be calculated by the earliest PFS event date.

A summary of censoring rules and the date of PD/death or censoring are given in Table 4.

Note that censoring overrides event in certain specified cases.

Table 4 Summary of Censoring Rules for PFS

Situation	Date of PD/Death or Censoring	PFS Outcome
Documented Progressive Disease (PD) or death in the absence of progression	Date of earliest documentation of PD or date of death	Event
Either no assessment at baseline or no evaluable assessments post-baseline AND death prior to Year 1 scheduled post-baseline disease assessment	Date of death	Event
Either no assessment at baseline or no evaluable assessments post-baseline AND no death prior to Year 1 scheduled post-baseline disease assessment	Date of first dose (Day 1)	Censored
PD or death (in the absence of progression) 57 weeks since previous disease assessments	Last evaluable progression-free disease assessment prior to missed assessments	Censored
At least one post-baseline tumor assessment, On- going with neither PD nor death at the time of analysis or lost to follow-up or withdrawn consent	Date of last evaluable disease assessment	Censored
Initiation of subsequent anticancer, excluding BM transplantation treatment prior to PD or death	Date of last evaluable disease assessment prior to initiation of subsequent anticancer treatment	Censored

Abbreviations: BM bone marrow, PD, progressive disease; PFS, progression-free survival

If response is defined as CR or PR, provided the participant did not receive any new anti-cancer treatment for Hodgkin lymphoma from the last dose of sabestomig and start of the preconditioning for the BM transplantation. If the participant received any new treatment (before the BM transplantation), he would follow the censoring rules for new treatment for Hodgkin lymphoma. The information will be collected in the EDC.

Radiotherapy consolidation for a participant in complete response is not considered a subsequent anticancer treatment.

The PFS time is always derived based on scan/assessment dates, not visit dates. Disease assessments/scans contributing towards a particular visit may be performed on different dates. The following rules are applied:

 The date of progression is determined based on the earliest of the dates of the component that triggered the progression.

Note: for target lesions only the latest scan date is recorded out of all scans performed at that assessment for the target lesions and similarly for non-target lesions only the latest scan date is recorded out of all scans performed at that assessment for the non-target lesions.

Duration of follow-up for PFS is applicable only for PFS censored participants and is defined as follows:

Duration of follow-up for PFS in censored participants (months) = (date of PFS event [progression/death] or censoring – date of first dose + 1) / (365.25/12).

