4.2.4.2 Derivations

DoR (months) = (date of progression free survival [PFS] event [progression/death] or censoring – date of first objective response + 1) / (365.25/12).

The end of response should coincide with the date of progression or death from any cause used for the PFS endpoint. The time of the initial response is defined as the latest of the dates contributing towards the first visit response of CR or PR. If a participant does not progress following a response, then their DoR is censored on the PFS censoring date. Only participants who have achieved objective response are evaluated for DoR.

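### SAP 4.2.6 gives conflicting PFS rules for missed scans, deaths without scans and deaths after transplant in response; the first and third conflicts reach DoR and DoCR

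*SAP*

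**What the plan says.** **Missed scans.** The text of SAP 4.2.6.2 says that "if the participant progresses or dies immediately after two or more consecutive missed visits, the participant is censored" at the last evaluable assessment before the gap. It sets no time limit and does not restrict the rule to one phase. The matching row of Table 4 reads "PD or death (in the absence of progression) 57 weeks since previous disease assessments".

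**No baseline scan, or no evaluable scan afterwards.** The text censors at Day 1 "unless they die within 57 weeks (i.e, 2 missed visit after Year 1 whereby disease assessments are every 6 months", in which case the death is an event. Table 4 makes such a death an event only if it precedes the Year 1 assessment. Its other row, "AND no death prior to Year 1 scheduled post-baseline disease assessment", censors at first dose.

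**Transplant in response.** SAP 4.2.6.1 counts death "by any cause in the absence of disease progression or subsequent anticancer treatment or bone marrow transplantation in response". The first row of Table 4 makes any death without progression an event. The new-therapy censoring row is worded "Initiation of subsequent anticancer, excluding BM transplantation treatment prior to PD or death", so transplant does not trigger it.

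**Link to DoR and DoCR.** SAP 4.2.4.2 says: "The end of response should coincide with the date of progression or death from any cause used for the PFS endpoint". SAP 4.2.5.2 repeats this for DoCR and adds: "If a participant does not progress following a response, then their DoCR is censored on the PFS censoring date".

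**The concern.** The text and the table are both operative. Table 4 is introduced as a summary, but the censoring date for new therapy appears only there, so a programmer cannot ignore it. Two programmers who each follow the SAP faithfully could give the same participant an event or a censored time, many months apart.

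PFS is a secondary endpoint with 12- and 24-month landmarks, and DoR and DoCR take their end dates from it. If the rules stay in conflict, the choice may be made after the data have been seen.

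**Working it through.** **Inputs**
- Threshold (SAP 4.2.6.2): 2 × 26 + 5 = 57 weeks, which reproduces; 57 × 7 = 399 days.
- Before Year 1 there are three cycle-based scans, each at least 10 days after dosing (SAP Appendix B 1; cycle numbers redacted).
- Year 1 and later scans are timed from first dose, ±2 weeks (Protocol Table 16, footnote c). An on-time Year 1 scan falls on days 351–379, and the 24-month window closes on day 730 + 14 = 744.
- SAP Appendix B 1 windows: Year 1, days 314–455; 1.5 years, 456–638; 2 years, 639–821.
- Months = days / (365.25/12) = days / 30.4375, with first dose as day 1.
- Scan 1 is assumed on day 53: Cycle 3 Day 1 is day 43, plus 10. Protocol Appendix L mentions a Cycle 3 response assessment. The range runs from day 11 (Cycle 1 plus 10 days, the theoretical earliest) to day 70 (the 10-week limit for the interim response-evaluable set, Protocol 9.3).
- The comparison sign in the 57-week row is not legible in the text available. The row is read as a gap beyond 57 weeks; no example sits at the boundary.

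**Conflict 1, before Year 1.** Scan 1 is done, scans 2 and 3 are missed, and progression is found at an on-time Year 1 scan. The longest possible gap is 379 − 11 = 368 days (52.6 weeks), below 399. The Table 4 row cannot fire, yet two scans were missed. All 680 ways of choosing three scan cycles from Cycles 1–17 give this result, so the redaction does not matter. A late scan at the end of the Appendix B Year 1 window can exceed the limit: 455 − 11 = 444 days (63.4 weeks).

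With scan 1 on day 53 and progression on day 365:
- Text: PFS censored at 53 / 30.4375 = 1.74 months (range 0.36 to 2.30).
- Table 4: event at 365 / 30.4375 = 11.99 months.
- If scan 1 was also the first response, DoR by the text is censored at 1 / 30.4375 = 0.03 months. By Table 4 it is an event at (365 − 53 + 1) / 30.4375 = 10.28 months (range 9.72 to 11.66).

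**Conflict 1, after Year 1.** The rules differ in both directions:

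| Windows | Last scan | Missed | Outcome | Gap | Text | Table 4 |
|---|---|---|---|---|---|---|
| Protocol | day 365 | 18 and 24 months | death day 760 | 395 d, 56.4 wk | censored | event |
| Appendix B | day 455 | 1.5 and 2 years | death day 822 | 367 d, 52.4 wk | censored | event |
| Appendix B | day 351 | 1.5 years only | progression day 760 | 409 d, 58.4 wk | event | censored |

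In the first row, PFS is censored at 11.99 months or is an event at 760 / 30.4375 = 24.97 months. With a last scan at Year 1, two scans missed and progression found at 2.5 years, the gap is 913 − 365 = 548 days and both rules censor.

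No window is tied to a missed visit. SAP 3.3.2 assigns scans by protocol windows; Appendix B 1 gives much wider ones.

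**Conflict 2.** The text's cut-off is day 399; Table 4's is the Year 1 assessment. The disputed period depends on which day that means:
- Day 365: 399 − 365 = 34 days
- Day 351: 48 days
- Day 379: 20 days
- Day 314: 85 days
- Day 455: reversed, 455 − 399 = 56 days

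With day 365, such a death is an event at 12.0 to 13.1 months or is censored at Day 1. For example, a death on day 385 is an event at 12.65 months or is censored at 0.03.

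**Conflict 3.** A responder has a transplant with no intervening therapy and dies without progression. SAP 4.2.6.1 says this is not an event. Table 4's first row says it is, and its last row does not censor. If the definition governs, no row supplies a censoring date. SAP 4.2.4.1 and 4.2.5.1 end DoR and DoCR at death from any cause, with no transplant exception. The PFS definition in Protocol 9.4.2.2 has no transplant clause either.

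**Carry-over.** Conflicts 1 and 3 reach DoR and DoCR through the PFS date. Conflict 2 does not, because a responder has an evaluable post-baseline scan and the response-evaluable set requires measurable disease at baseline.

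**The case against.** The best defence is that SAP 4.2.6.2 has its own tie-break: where several censoring conditions are met, the earliest applies, and censoring overrides an event in certain cases. If text and table conditions are pooled, every missed-scan example is censored and the no-scan death is censored at Day 1. That reading fails in three ways. It cancels the text's express statement that the no-scan death is an event. It censors after one missed scan (days 351 and 760), against the text's own two-visit rule. It gives no date for the transplant case.

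A second defence is the note under Table 4, which treats transplant in response separately. That note defines when a transplant counts as in response and sends other transplants to the new-therapy rule. It does not say whether a later death is an event. With the DoR and DoCR definitions and the continued collection of post-transplant disease status, it does favour counting the death. The transplant clause in SAP 4.2.6.1 may then be a stray phrase, but it is still there.

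Other points stand. Conflict 2 is narrow, and Table 4 may simply have dropped the 5-week late allowance; the day-314 and day-455 readings treat window limits as the scheduled date. The day-455 scan is an extreme case. The pre-Year-1 month values rest on an assumed scan day. The 3.3.2 windows serve by-visit summaries, and PFS uses scan dates, which leaves a missed visit with no defined window. Conflict 3 concerns deaths only. The study has no hypothesis tests or cohort comparisons.

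**Conclusion.** Wrong as written: these are contradictory rules, not missing detail. Conflict 1 is the largest, moving PFS in the worked case between censored at 1.7 months (0.4 to 2.3 across the assumed scan days) and an event at 12.0. That it occurs before Year 1 does not depend on the redacted cycle numbers. Conflict 2 covers about 34 days with Year 1 at day 365. Conflict 3 is an event on the death date, or censoring at a date the SAP does not give.

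These are contrasts for single participants, not expected effects on a median or landmark. How many participants are affected cannot be computed from the documents. PFS, DoR and DoCR are descriptive secondary endpoints; ORR, CRR and the futility rules are unaffected. The point should be fixed before analysis, but it does not threaten the primary results.

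**What to change.** 1. Use one missed-assessment rule in text and table. Replace the flat 57-week row with at least two scheduled disease assessments missed in a row, for progression and death alike, before and after Year 1. Name one set of scan windows for judging a missed assessment, and reconcile SAP 3.3.2 with Appendix B 1. Alternatively, set time limits for each phase of the schedule and use the same limits in both places.
2. For deaths without usable scans, give one cut-off, stated as a study day, in both places.
3. State in 4.2.6.1 and Table 4 whether a death after transplant in response is an event or is censored and, if censored, at what date. Apply the same rule to DoR and DoCR. The choice is the sponsor's.

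The cost is SAP wording and programming, with no new data and no change to study conduct.

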4.2.6.3 Analysis of Secondary Endpoint: PFS

The main analysis of PFS is based on the FAS. The number and percentage of participants experiencing a PFS event (broken down by type of event/censoring) and Kaplan-Meier plots of PFS, for dose levels with at least participants may be presented. The median PFS and its two-sided 95% CI will be estimated using the Kaplan-Meier method (if participant numbers allow).

The intervention status at progression of participants at the time of analysis will be summarized. This includes the number (%) of participants who were on intervention at the time of progression, the number (%) of participants who discontinued study intervention prior to progression, the number (%) of participants who have not progressed and were on intervention or discontinued intervention.

A summary of the duration of follow-up for PFS is included using median (range). This will be presented for censored participants (including all types of PFS censoring).

The proportion of participants alive and progression free at 3, 6, 12, 18 and 24 months and associated two-sided 95% CI will be estimated using the Kaplan-Meier method. Other landmark rates may be considered per sponsor discretion.

4.2.6.4 Supportive Analysis of PFS Endpoint

A supportive analyses of PFS for Part B will be presented using Investigator responses and based on modified Lugano criteria and RECIL. Data will be recorded in eCRF.

4.2.7 Secondary Endpoint: Overall Survival (OS)

OS is a secondary efficacy endpoint.

4.2.7.1 Definition

OS is defined as the time from the date of first dose until death due to any cause regardless of whether the participant withdraws from study therapy or receives another anti-cancer therapy.

4.2.7.2 Derivations

OS (months) = (date of death or censoring – date of first dose + 1) / (365.25/12).

Any participant not known to have died at the time of analysis will be censored based on the last recorded date on which the participant was known to be alive. Participants known to be alive or dead after the data cut-off for analysis will be censored at the DCO. Participants lost

to follow-up will be censored at the date the participant is last know known to have been alive

Note: Survival follow-up calls will be made in the week following the date of DCO for the analysis, and if participants are confirmed to be alive or if the death date is post the DCO date these participants will be censored at the date of DCO. The status of ongoing, withdrawn (from the study) and "lost to follow-up" participants at the time of the final OS analysis should be obtained by the site personnel by checking the participant's notes, hospital records, contacting the participant's general practitioner and checking publicly-available death registries. In the event that the participant has actively withdrawn consent to the processing of their personal data, the vital status of the participant can be obtained by site personnel from publicly available resources where it is possible to do so under applicable local laws.

Note: For any OS analysis performed prior to the final OS analysis, in the absence of survival calls being made, it may be necessary to use all relevant eCRF fields to determine the last recorded date on which the participant was known to be alive for those participants still on intervention (since the SURVIVE module is only completed for participants off intervention if a survival sweep is not performed). The last date for each individual participant is defined as the latest among the following dates recorded on the eCRFs:

- AE start, stop and change in severity dates
- Admission and discharge dates of hospitalization
- Study intervention date
- End of intervention date
- Concomitant medication start and stop dates
- Laboratory test dates
- Date of vital signs
- Disease assessment dates on eCRF
- Start and stop dates of alternative anticancer intervention
- Date last known alive on survival status eCRF
- End of study date

Duration of follow-up for OS is reported separately for censored participants and non-censored participants is defined as follows:

Duration of follow-up for OS (months) = (date of death or censoring (date last known to be alive) – date of first dose + 1) / (365.25/12).

4.2.7.3 Handling of Dropouts and Missing Data

If a participant is known to have died where only a partial death date is available, then the date of death is imputed as the latest of the last date known to be alive +1 from the database and the death date using the available information provided:

- For Missing day only using the 1st of the month of death.
- For Missing day and Month using the 1st of January of the year of death.

If there is evidence of death but the date is entirely missing, it is treated as missing, ie, censored at the last known alive date.

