## 7.3 Lost to Follow-up

A participant will be considered lost to follow-up if the participant repeatedly fails to return for scheduled visits and is unable to be contacted by the study site.

The following actions must be taken if a participant fails to return to the clinic for a required study visit:

- The site must attempt to contact the participant and reschedule the missed visit as soon as possible and counsel the participant on the importance of maintaining the assigned visit schedule and ascertain whether or not the participant wishes to and/or should continue in the study.
- Before a participant is deemed lost to follow-up, the Investigator or designee must make every effort to regain contact with the participant (where possible, 3 telephone calls and, if necessary, a certified letter to the participant's last known mailing address or local equivalent methods). These contact attempts should be documented in the participant's medical record.
- Should the participant continue to be unreachable, the participant will be considered to have withdrawn from the study.

Site personnel, or an independent third-party, will attempt to collect the vital status of the participant within legal and ethical boundaries for all participants who received any dose of study intervention. Public sources may be searched for vital status information. If vital status is determined as deceased, this will be documented, and the participant will not be considered lost to follow-up. AstraZeneca personnel will not be involved in any attempts to collect vital status information.

Discontinuation of specific sites or of the study as a whole are handled as part of Appendix A.

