#### **Overall Survival**

The OS is defined as the time from the start of treatment until death due to any cause regardless of whether participant withdraws from treatment or receives another antilymphoma therapy. Any participant not known to have died at the time of analysis will be censored based on the last recorded date on which the participant was known to be alive.

Note: Survival follow-up phone calls will be made in the week following the date of DCO for the analysis, if participants are confirmed to be alive or if the death date is after the DCO date the participants will be censored at the date of DCO.

The OS data will be presented similarly to the presentation described for PFS.

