4.2.7.4 Primary Analysis of Secondary Endpoint (Overall Survival)

[figure not shown]
The analysis of OS is based on the FAS. The number and percentage of participants experiencing an OS event and Kaplan-Meier plots, for dose levels with at least participants of OS may be presented. The median OS and two-sided 95% CI will be estimated using the Kaplan-Meier method (if participant numbers allow).

Summaries of the number and percentage of participants who have died, those still in survival follow-up, those lost to follow-up and those who have withdrawn consent will be provided.

A summary of the duration of follow-up for OS will be included using median (range). This will be presented for censored participants.

The proportion of participants alive at 6, 12, 18 and 24 months and associated two-sided 95% CI will be estimated using the Kaplan-Meier method.

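### The SAP censors a known death that has no date at all, against its own OS definition; if any such death occurs, OS is biased upward

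*SAP*

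**What the plan says.** The SAP defines the endpoint in 4.2.7.1: "OS is defined as the time from the date of first dose until death due to any cause". Its general censoring rule in 4.2.7.2 reads: "Any participant not known to have died at the time of analysis will be censored based on the last recorded date". Protocol 9.4.2.2 (Overall Survival) has the same rule, "Any participant not known to have died at the time of analysis will be censored", and makes no exception for a missing death date.

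SAP 4.2.7.3 then treats two kinds of incomplete date differently:

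- **Partial date (month or year known).** The death stays an event: "the date of death is imputed as the latest of the last date known to be alive +1 from the database and the death date", with the first of the month or 1 January filled in. SAP 3.3.6 repeats this rule and gives none for a fully missing death date.
- **No date at all.** Where death is evident but undated, "it is treated as missing, ie, censored at the last known alive date".

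The results feed the landmarks in SAP 4.2.7.4: "The proportion of participants alive at 6, 12, 18 and 24 months and associated two-sided 95% CI will be estimated using the Kaplan-Meier method". Protocol Table 6 names the 12- and 24-month landmarks as part of the secondary endpoint. SAP 4.2.7.4 also reports how many participants have died, separately from the number of OS events.

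**The concern.** Under this rule the reason for censoring is the event itself. Kaplan-Meier estimation assumes that a censored participant has the same outlook as those still at risk. Here the outlook is known, and it is death, so any error favours the drug.

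The rule is also inconsistent within one section. A participant whose year of death is known is an event; lose the year, and the same participant becomes a censored observation. The count of deaths and the count of OS events in SAP 4.2.7.4 could then disagree.

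Undated deaths are possible in this design. Protocol Table 4 sets survival contact at six-month intervals and allows telephone or email. Protocol 7.1 allows information from relatives or treating physicians, and Protocol 7.3 adds: "Public sources may be searched for vital status information". That the SAP has a rule for the case shows its authors foresaw it.

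**Working it through.** The plan states no OS rate, event count or power, so there is no figure to reproduce. Two checks show the scale.

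**1. One undated death, exact algebra.** Take n participants with no other censoring before the landmark. Let j be the deaths up to the affected last-known-alive date, and d the deaths by the landmark, counting the undated one as an event one day after that date.

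- Death kept as an event: S = (n − d)/n.
- SAP rule: S = (n − j)/n × (n − d)/(n − j − 1).
- Difference: (n − d)/n × 1/(n − j − 1).

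Since d is at least j + 1, the difference is never negative here and never exceeds 1/n. It equals 1/n when no other death falls between the last contact and the landmark. At an assumed n = 50 with d = 25:

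- j = 24: 25/50 × 1/25 = 2.0 points.
- j = 0: 25/50 × 1/49 = 1.0 point.

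A landmark before the last-known-alive date does not move. If many participants are censored earlier, fewer are at risk and one death can weigh more than 1/n. That is plausible by month 24, because Protocol 9.4.1 allows the final analysis 6 months after the last participant starts.

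Simulated single cases (one such death by month 24, assumed cohort sizes, median OS 24 or 48 months) gave these mean shifts in points:

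| n | 12 months | 24 months | largest |
|---|---|---|---|
| 30 | 1.5–1.6 | 2.2–2.7 | 3.3 |
| 50 | 0.9–1.0 | 1.3–1.6 | 2.0 |
| 80 | 0.6 | 0.8–1.0 | 1.25 |

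The 12-month estimate did not move in about 40–46% of these runs. No run moved either landmark down.

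**2. A share q of deaths undated.** This used 400,000 exponential survival times with medians of 24 and 48 months, the historical range in Protocol 2.2.2. Assumptions not in the documents: q itself, with undated deaths arising at random; last contact 3-weekly or 6-monthly; censoring at 30 months, or uniform over 6–30 months. Overstatement under the SAP rule, in points at 12 / 24 months:

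| q | median 24 months | median 48 months |
|---|---|---|
| 0% | 0 / 0 | 0 / 0 |
| 2% | 0.4–0.5 / 0.6–0.7 | 0.3 / 0.5 |
| 5% | 1.1–1.2 / 1.6–1.8 | 0.7 / 1.2 |
| 10% | 2.3–2.5 / 3.3–3.6 | 1.4–1.5 / 2.4–2.5 |
| 20% | 4.7–5.0 / 6.9–7.4 | 2.9–3.0 / 4.9–5.1 |

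With the death kept as an event one day after last known alive, the bias lies between −0.2 and +0.9 points in every scenario, and between −0.1 and +0.4 up to q = 10%. The simulated 6-monthly contacts fall exactly on months 12 and 24. Were they elsewhere, this rule would date some deaths too early and lower a landmark slightly.

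**The case against.** The strongest reply is that the rule may never be used. Not even the year of death may be known, and the plan works against that:

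- SAP 4.2.7.2 calls for survival calls in the week after the data cut-off. Before the final OS analysis, sites check notes, hospital records, general practitioners and death registries.
- Protocol 8.3.2 collects the date of death for SAEs, and Protocol 8.3.12 has deaths documented in the eCRF, including those after safety follow-up.
- Six-monthly contact brackets a death, so the year will often be known.
- The effect would be visible, because SAP 4.2.7.4 and 4.5.3 report deaths separately.

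All of this stands as a limit on frequency and size. None of it makes the rule correct once it is triggered.

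It can also be said that the protocol is silent on missing death dates and that Protocol 9.4.1 leaves missing data to the SAP. So this is not a clean breach of the protocol. The firmer conflict is within the SAP, between 4.2.7.3 and both 4.2.7.1 and 4.2.7.2.

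A reader might infer that reported OS is overstated as a matter of fact. The documents do not support that: no undated death is recorded or predicted. Nor can the effect be sized from the 52 participants allowed in Part A (SAP 3.3.7), because efficacy is presented by dose level or cohort and no planned OS analysis has that denominator. The heading for an OS sensitivity analysis (SAP 4.2.7.5) has no text below it; that may be redaction and is not held against the plan.

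**Conclusion.** The rule is wrong as written, and its effect is conditional. Censoring a participant known to be dead contradicts the SAP's definition of the event, its general censoring rule and its own handling of partial dates. Any bias it causes in OS is upward.

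The likely size is small. It is zero with no undated death. Otherwise it is at most about 1/n per such death in the dose level or cohort analysed, provided little censoring has come before. At 5% or fewer of deaths undated, the illustration gives at most about 1.2 points at 12 months and 1.8 at 24. These figures rest on assumed cohort sizes, an assumed share of undated deaths and exponential survival.

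OS is a descriptive secondary endpoint. Protocol 9.1 plans no hypothesis tests, and the No-Go and futility rules in Protocol 9.5 use response rates, so no decision rule changes. The case for acting is that the correction is nearly free and is better made before database lock than after undated deaths are known.

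**What to change.** Replace the last sentence of SAP 4.2.7.3 with a rule to this effect: a participant known to have died on or before the data cut-off, with no death date, is an OS event on the last known alive date plus one day. This extends the fallback already used for partial dates. The cut-off condition is needed because calls in the following week may find an undated death that cannot be placed before or after the cut-off; list such cases separately.

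Also:

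- Flag each imputed date and report the number of such deaths by dose level or cohort.
- Give two sensitivity analyses: the present censoring rule, and a later death date (the midpoint, or the day the site learned of the death, capped at the data cut-off).

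Do not carry the rule over to PFS, DoR or DoCR as it stands. Under SAP 4.2.6.2, whether a death counts as a PFS event can depend on how long after the last assessment it occurred, so an imputed date could itself decide the outcome. Those rules would have to be reconciled first.

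The cost is one SAP sentence, one count and two short reruns. The downside is that last known alive plus one day is the earliest possible date, so OS may be slightly conservative; the later-date analysis shows by how much.
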